2. INTRODUCTION

2.1 Background and rationale for conducting this study

Study D419QC00002 is an open-label, multicenter, multi-arm, Phase II study in patients with extensive-stage small cell lung cancer (ED-SCLC) who have refractory or resistant disease, defined as patients who progress during first-line platinum based chemotherapy or those who progress within 90 days after completing first-line platinum based chemotherapy. Study D419QC00002 is modular in design, allowing evaluation of the safety, tolerability, pharmacokinetics (PK) and anti-tumor activity of different combinations of novel anti-cancer agents in patients with refractory or resistant ED-SCLC, and will consist of a number of study arms, each evaluating the safety and tolerability of a specific combination.

Arm B in Study D419QC00002 investigates the efficacy, safety, and tolerability of treatment with oral AZD1775 (PO) in combination with intravenous (IV) carboplatin (CBDP) in ED-SCLC patients.

The rationale for conducting this study is in Section 2.2 of the master protocol.

2.2 AZD1775

AZD1775 is a highly selective, ATP competitive, small-molecule inhibitor of the WEE1 kinase that sensitises tumour cells to cytotoxic agents and is being developed for the treatment of patients with advanced solid tumours with genetic deficiencies in DNA repair mechanisms. Inhibition of the DNA damage checkpoint kinase WEE1 potentiates genotoxic chemotherapies by abrogating cell-cycle arrest and eliminating the opportunity for proper DNA repair to occur. From a therapeutic standpoint, inhibition of checkpoint kinases that mediate cell-cycle arrest may force tumor cells to continue cell division before chemically induced DNA damage is repaired, eventually causing apoptosis or mitotic catastrophe (Medema and Macurek 2012).

In *in vitro* studies, AZD1775 inhibits WEE1 activity and induces DNA damage as well as G2 checkpoint escape in cell-based assays. AZD1775 increases cytotoxicity when used in combination with other DNA damaging agents, such as gemcitabine (GEMZAR[®]), cisplatin (Platinol[®]), and topotecan (HYCAMTIN[®]) in tumor protein 53 (p53)-deficient cell lines. In *in vivo* studies, AZD1775 was well tolerated and showed enhancement of anti-tumor efficacy by gemcitabine, CBDP, cisplatin, 5-fluorouracil (5-FU), and capecitabine (XELODA[®]) in nude rat xenograft tumor models. Similarly, in nude mouse xenograft models, AZD1775 treatment resulted in significant tumor growth inhibition at tolerated doses, and also enhanced the anti-tumor growth effect of gemcitabine, CBDP, and radiation therapy (see most recent AZD1775 Investigator's Brochure [IB]).

Small cell lung cancers (SCLCs) harbor multiple genomic alterations involved in cell cycle regulation, oncogenic signaling, and double-strand break repair. The most common genetic alterations in SCLC occur in: pTP53 (90%), retinoblastoma 1 (RBI, 85%) [Byers et al 2012], MYC (cMYC, MYCN, and MYCL1 ~5% each), RAS (2%), and BRCA1/2 (3%). These alterations, and in particular, combinations of these alterations, force cancer cells to depend on

the G2-M checkpoint for restoring cell cycle function and division. It is estimated that 18% of SCLCs harbor mutations in cell cycle regulation (TP53) and in oncogenic signalling (MYC or RAS). Likewise, 3% of SCLCs harbor mutations in both cell cycle regulation (TP53) and DSB repair (BRCA1/2).

The high unmet medical need and prevalence of somatic alterations affecting cell cycle control and DNA repair make SCLC an important cancer setting to investigate AZD1775.

2.3 Carboplatin

CBDP is a second-generation platinum containing chemotherapeutic compound, and an analog of cisplatin. While cisplatin has two chloride groups, CBDP possesses a cyclobutane dicarboxylate (CBDCA) moiety. This results in lower reactivity and DNA binding kinetics, though the same platinum-DNA adducts are formed as those induced by cisplatin. CBDP however demonstrates less nephrotoxicity and neurotoxicity, and is less emetogenic than its parent compound cisplatin.

CBDP and etoposide (ETOPOPHOS[®]) or cisplatin and etoposide are the most commonly used chemotherapy regimen in the treatment of SCLC; CBDP is used more often than cisplatin in order to reduce the risk of emesis, neuropathy, and nephropathy (NCCN 2015).

2.4 Rationale for study design, doses, and control groups

The rationale for the unmet medical need in refractory or resistant ED-SCLC is described in Section 2.2.1 of the master protocol. The rationale for the specific study design aspects of Arm B is described below.

2.4.1 AZD1775 in combination with CBDP

Tumor cells rely on cell cycle checkpoints for repair of DNA damage induced by cytotoxic agents. As AZD1775 selectively inhibits WEE1, it effectively disrupts the regulation of cell cycle checkpoints, particularly the G2 checkpoint. Because cell cycle checkpoints are critical in the DNA damage response, AZD1775 can potentiate the activity of cytotoxic agents and thus acts to sensitize the tumor cell to the cytotoxic agent. Non-clinical studies have demonstrated that WEE1 effectively sensitizes tumor cells to cytotoxic effects of gemcitabine, cisplatin, or CBDP (refer to most recent AZD1775 IB). This has also been demonstrated clinically in platinum refractory ovarian cancer with objective response rate (ORR) as high as 41% (Leijen et al 2015).

2.4.2 Clinical experience with AZD1775

AZD1775 has been investigated in 12 AstraZeneca-sponsored or CCI clinical studies, 6 of which are ongoing. As of 11 November 2015, a total of approximately 443 patients have been exposed to AZD1775 in AstraZeneca-sponsored or CCI clinical studies. In addition, approximately 200 patients have also received AZD1775 as part of externally-sponsored scientific research. These patients have received single doses per cycle as high as 1300 mg of AZD1775 as monotherapy, 325 mg of AZD1775 in a single-dose in combination with chemotherapy, and 325 mg twice daily (BID) in a multiple-dose regimen

in combination with chemotherapy. For details on those studies, and for complete summary of the clinical safety and efficacy profile of AZD1775, refer to the current IB.

The most common adverse events (AEs) observed in studies of AZD1775 combined with chemotherapy include blood and lymphatic disorders, (ie, thrombocytopenia, neutropenia, leukopenia, anemia, and febrile neutropenia), gastrointestinal disorders (ie, diarrhea, vomiting, nausea, abdominal pain, and constipation), and blood investigations (ie, hematology and serum chemistries). Other reported safety concerns include electrocardiogram (ECG) QT prolongation, fatigue, influenza-like illness, malaise, mucosal inflammation, myalgia, palpitations, pruritus, pyrexia, rash, rash maculopapular, skin lesion, stomatitis, tachycardia, and loss of weight.

The single-dose maximum tolerated dose (MTD) for both the gemcitabine and cisplatin combination therapies was 200 mg of AZD1775 in this study (NCT00648648). Dose-limiting toxicities (DLTs) tended to be hematological in nature in the gemcitabine group and constitutional in the cisplatin group. The single-dose MTD for the combination with CBDP was 325 mg of AZD1775. DLTs in this group were related to serum chemistry.

DLTs observed in the multiple-dose CBDP combination have been both hematological and constitutional in nature. The multiple-dose MTD in combination with CBDP is AZD1775 225 mg BID \times 5 for 2.5 days. Hematologic DLTs were most commonly observed in the multiple-dose AZD1775 combination treatment groups with gemcitabine and cisplatin. A MTD of AZD1775 in combination with gemcitabine was established with an interim dose of 50 mg BID on Day 1, 25 mg BID on Day 2, and 25 mg on Day 3. An attenuated once daily (QD) for 2-day schedule in combination with gemcitabine was investigated. Two DLTs (Grade 3 febrile neutropenia and Grade 3 aspartate aminotransferase and alanine aminotransferase (AST/ALT) increase) were observed at 200 mg QD for 2 days with the regimen in combination with gemcitabine. The dose was adjusted to 175 mg QD for 2 days and was determined to be the MTD. The MTD for combination with cisplatin has been exceeded at the 250 mg dose level, and tolerability of the MTD at 200 mg BID \times 5 for 2.5 days has been confirmed.

The MTD for AZD1775 in combination with 5-FU was not reached due to early study termination. DLTs of encephalopathy and hyponatremia were observed in the AZD1775 20 mg BID in combination with 1000 mg/m² 5-FU treatment group.

Triplet-based therapy of AZD1775, CBDP, and paclitaxel was administered in study NCT01357161: a Phase II study evaluating AZD1775 combined with CBDP and paclitaxel (ABRAXANE[®]) in patients with platinum-sensitive p53-mutant ovarian cancer. The starting dose of 225 mg AZD1775 (BID for 5 total doses) in Part 1 (an open-label dose escalation/de-escalation study that employed a toxicity probability design to evaluate the safety and tolerability of the triplet combination) was generally well-tolerated. One patient experienced a DLT in the first 6 patients treated, and the dose remained at 225 mg BID for 2.5 days. A total of 15 patients were treated with 3 DLTs being reported (Grade 3 and 4 febrile neutropenia and Grade 4 thrombocytopenia). Other toxicities were generally blood and lymphatic system disorders and gastrointestinal disorders. Of the 14 evaluable patients by

Response Evaluation Criteria in Solid Tumors (RECIST 1.1) in Part 1, there were 11 PRs (6 confirmed and 5 unconfirmed), and 3 stable diseases (SDs); 7 patients were evaluable by CA-125 with 3 CRs and 4 PRs. All patients were treated at the 225 mg AZD1775 BID 2.5 day dose level in combination with paclitaxel and CBDP. The dose established in Part 1 was determined to be the recommended Phase II dose. Part 2 of the study compared the administration of AZD1775 at the recommended Phase II dose versus placebo in combination with CBDP AUC 5 and paclitaxel 175 mg/m² in a double-blind fashion. Part 2 of the study is completed and showed the below final safety and efficacy data summary. As of 11 November 2015, a total of 59 patients were treated in the AZD1775 combination with paclitaxel and CBDP arm, and the following grade ≥ 3 AEs were reported: 21 (35.6%) neutropenia, 12 (20.3%) anemia, 12 (20.3%) thrombocytopenia, 6 (10.2%) diarrhea, 6 (10.2%) vomiting, and 3 (5.1%) nausea; compared to placebo and CBDP arm (n=60) with the following grade ≥ 3 AEs reported: 20 (33.3%) neutropenia, 7 (11.7%) thrombocytopenia, 4 (6.7%) anemia, 2 (3.3%) diarrhea, 2 (3.3%) alopecia, 1 (1.7%) nausea, and 1 (1.7%) vomiting.

For enhanced RECIST, median progression-free survival (PFS) for patients receiving AZD1775 plus chemotherapy was 34.14 weeks compared to 31.86 weeks for those receiving chemotherapy alone (hazard ratio 0.63 80% CI [0.45,0.89], p=0.080) [Oza et al 2015]. The combination of AZD1775 with topotecan and cisplatin in adult patients with cervical cancer (study NCT01076400) was evaluated. Toxicities were generally hematological and gastrointestinal in nature. No unexpected toxicities were observed.

Available preliminary efficacy data are encouraging, with confirmed partial responses (PRs) in patients participating in the 2 ovarian cancer trials, as well as the first time in human (FTIM) Phase I trial in solid tumors. Several studies are ongoing (AZD1775 IB).

2.4.3 Pharmacokinetic and pharmacodynamic data

The PK data of AZD1775 following a single oral administration showed a moderate rate of absorption with a maximum plasma drug concentration at steady state (C_{max}) occurring at 3 to 4 hours. Post-peak plasma concentrations declined essentially in a mono-exponential manner with a half-life in the region of 10 hours. Exposure as measured by C_{max} and area under the curve $AUC_{(0-\infty)}$ increased in a dose-proportional manner over the dose range of 325 to 1300 mg. Following single (100 to 325 mg) and multiple dose administrations of AZD1775 (25 to 325 mg BID and 100 to 200 mg QD) with CBDP, cisplatin, and gemcitabine, plasma exposure of AZD1775 was consistent with predictions based on the single-dose regimen. Preliminary investigation of drug-drug interactions (DDI) in the FTIM study (NCT00648648) suggests a 40% to 60% increase in the exposure of AZD1775 in the presence of aprepitant (moderate CYP3A4 inhibitor), but no effect with the concomitant administration of steroids (moderate CYP3A4 inducers). Preliminary studies also suggested that the Premarketed Oral Formulation (PMF) of AZD1775 was similar to that of the Fit-For-Purpose (FFP) formulation. Based on the preliminary comparison of the results of AZD1775 PK parameters at the 225 mg dose, PK estimates in Asian patients were 30% to 45% higher than in Western patients.

Pharmacodynamic analyses have mainly focused on CDK-1. By inhibiting WEE1, AZD1775 reduces phosphorylated CDK-1 levels relative to total CDK-1 with 125 mg BID of AZD1775 expected to be the threshold dose for target engagement.

Further information on the PK, metabolism, and pharmacodynamics effects of AZD1775 is provided in the current version of the AZD1775 IB.

2.4.4

CCI

CCI

2.4.5 Rationale for study endpoints

The rationale for study endpoints is provided in Section 2.2.3 of the master protocol.

2.5 Benefit/risk and ethical assessment

The unmet need in refractory or resistant ED-SCLC is described in Sections 2.1 and 2.3 of the master protocol. Additional information on the potential benefits of each agent (AZD1775 and CBDP) and an assessment of the potential and known risks can also be found in the current AZD1775 IB and in the manufacturer's label for CBDP ([Food and Drug Administration 2014](#)). Specific information relating to AZD1775 and CBDP is summarized below.

2.5.1 Potential benefits

2.5.1.1 AZD1775

AZD1775 has shown some clinical activity as monotherapy. Data is limited to 12 evaluable subjects from a Phase Ib study in advanced solid tumors (NCT02482311); CCI [REDACTED]

[REDACTED] In Part 1 of this study, confirmed PRs were observed in 2 patients carrying BRCA mutations: 1 with head and neck cancer and 1 with ovarian cancer. (Do et al, JCO, 2015)

2.5.1.2 CBDP

CBDP is registered for the treatment of ovarian cancer as monotherapy or in combination therapy for recurrent disease. CBDP is also used in the treatment of cancer of the lungs, testis, head and neck, and neuroblastoma. Additionally, CBDP in combination with etoposide is the standard first-line chemotherapeutic treatment of ED-SCLC (NCCN 2015).

2.5.1.3 AZD1775 + CBDP

AZD1775 in multiple-dose combination with CBDP: 44 out of 46 patients (CCI %) were evaluable for response. There was no confirmed PR observed in any of the evaluable patients. CCI [REDACTED]

[REDACTED] The most promising data comes from the recent Phase II study of AZD1775 + CBDP in patients with CCI [REDACTED]

[REDACTED] The median PFS was CCI months (Leijen et al 2015).

2.5.2 Identified and potential risks

2.5.2.1 AZD1775

No AZD1775 monotherapy studies have been completed, and there are limited data available on the administration of AZD1775 as a monotherapy. It has therefore not been possible to reliably estimate the frequency of occurrence of expected AEs and laboratory abnormalities for AZD1775 monotherapy.

Please refer to Section 5.4 ‘emerging safety profile’ of the current AZD1775 IB for complete list of events considered as identified risks, and Section 6 of IB ‘summary of data and guidance to investigators’ for information on the potential risks and risk mitigation strategy.

2.5.2.2 CBDP

Side effects of CBDP mainly consist of myelosuppression; especially thrombocytopenia, and leukopenia, nausea and vomiting, nephrotoxicity, liver toxicity (especially increased alkaline

phosphatase), ototoxicity and tinnitus, allergic reactions, neurotoxicity, alopecia, taste alterations, fever, and conjunctivitis.

2.5.2.3 AZD1775 + CBDP

The most common CCI

Preliminary PK analyses revealed that co-administration of CCI

2.5.3 Summary benefit: risk statement

The safety profile of AZD1775 when combined with CBDP has been shown to be acceptable, and AZD1775 has shown activity in several tumor types in the clinical development program to date. The potential benefit of this combination in ED-SCLC is unknown. Overall risks and benefits support the investigation of oral AZD1775 and carboplatin in patients with platinum refractory ED-SCLC according to this clinical protocol.

[figure not shown]
2.6 Study design

Arm B will investigate the preliminary efficacy, safety, and tolerability of AZD1775 (given PO) in combination with CBDP (given IV) to patients who progress during first-line chemotherapy (platinum refractory) or those who progress within 90 days after completing first-line chemotherapy (platinum resistant).

For Arm B, up to 20 eligible patients will be enrolled, and all patients will receive:

- AZD1775 225 mg BID PO for 2.5 days from Day 1 + CBDP AUC 5 Day 1 IV; every 3 weeks (q3w)

Appendix B Figure 1 Study design

BID Twice daily; CBDP Carboplatin; ED-SCLC Extensive-stage disease small-cell lung cancer; ORR Objective response rate; OS Overall survival; PFS Progression-free survival; PO By mouth; q3w Every 3 weeks.

3. STUDY OBJECTIVES

3.1 Primary objective

See Section 3.1 of the master protocol.

3.2 Secondary objectives

See Section 3.2 of the master protocol.

3.3 Safety objectives

See Section 3.3 of the master protocol.

3.4 Exploratory objectives

See Section 3.4 of the master protocol.

4. PATIENT SELECTION, ENROLLMENT, RANDOMIZATION, RESTRICTIONS, DISCONTINUATION, AND WITHDRAWAL

Each patient should meet all of the inclusion criteria and none of the exclusion criteria for this study. Under no circumstances can there be exceptions to this rule.

4.1 Inclusion criteria

1. Male or female ≥ 18 years at the time of screening.
2. Written informed consent and any locally required authorization (eg, Health Insurance Portability and Accountability Act in the US, EU Data Privacy Directive in the EU) obtained from the patient/legal representative prior to performing any protocol-related procedures, including screening evaluations.

3. Histologically or cytologically documented extensive disease American Joint Committee on Cancer Stage IV SCLC (T any, N any, M1 a/b) at initial diagnosis, also including patients with:
 - T3-4 due to multiple lung nodules that are too extensive or have tumor/nodal volume that is too large to be encompassed in a tolerable radiation plan.
 - Biopsy-proven mixed SCLC and NSCLC histology
 - Brain metastases; must be asymptomatic or treated and stable off steroids and anti-convulsants for at least 1 month prior to study treatment. Patients with suspected brain metastases at screening should have a computed tomography (CT)/magnetic resonance imaging (MRI) of the brain prior to study entry.
4. Patients must have demonstrated progressive disease (PD) either during first-line platinum-based chemotherapy (platinum refractory) or within 90 days of completing platinum-based chemotherapy (platinum resistant), and have not received further treatment apart from first-line platinum-based chemotherapy. Patients should be enrolled within 90 days of progression in order to be accepted into the study.
5. World Health Organization (WHO)/Eastern Cooperative Oncology Group (ECOG) Performance Status of 01 at enrolment- (see Section 6.3.1 of master protocol for ECOG assessment parameters)
6. At least 1 lesion, not previously irradiated, that can be accurately measured at baseline as ≥ 10 mm in the longest diameter (except lymph nodes, which must have a short axis ≥ 15 mm) with CT or MRI and that is suitable for accurate repeated measurements as per RECIST 1.1 guidelines.
7. Able and willing to swallow oral medication
8. Willingness and ability to comply with study and follow-up procedures.
9. Life expectancy of at least 8 weeks.
10. Adequate organ and marrow function as defined below;
 - Hemoglobin ≥ 9 g/dL
 - Absolute neutrophil count $\geq 1500/\mu\text{L}$ (use of granulocyte-colony stimulating factor is permitted)
 - Platelets $\geq 100000/\mu\text{L}$

- ALT and AST $\leq 3 \times$ upper limit of normal (ULN) or $\leq 5 \times$ ULN if known hepatic metastases
- Serum bilirubin within normal limits (WNL) or $\leq 1.5 \times$ the ULN in patients with liver metastases; or total bilirubin $\leq 3.0 \times$ ULN with direct bilirubin WNL in patients with well documented Gilbert's syndrome
- Serum creatinine $\leq 1.5 \times$ the ULN, or a calculated creatinine clearance (CrCl) ≥ 45 mL/min by the Cockcroft-Gault method:

$$\text{CrCl (glomerular filtration rate [GFR])} = \frac{(140 - \text{age}) \times (\text{weight/kg}) \times F^a}{(72 \times \text{serum creatinine mg/dL})}$$

^a where F= 0.85 for females and F=1 for males

11. Evidence of post-menopausal status or negative urinary or serum pregnancy test for female pre-menopausal patients. Women will be considered post-menopausal if they have been amenorrheic for 12 months without an alternative medical cause. The following age-specific requirements apply:

- Women <50 years of age would be considered post-menopausal if they have been amenorrheic for 12 months or more following cessation of exogenous hormonal treatments and if they have luteinizing hormone and follicle-stimulating hormone levels in the post-menopausal range for the institution or underwent surgical sterilization (bilateral oophorectomy or hysterectomy).
- Women ≥ 50 years of age would be considered post-menopausal if they have been amenorrheic for 12 months or more following cessation of all exogenous hormonal treatments, had radiation-induced oophorectomy with last menses >1 year ago, had chemotherapy-induced menopause with >1 year interval since last menses, or underwent surgical sterilization (bilateral oophorectomy or hysterectomy).

Females of childbearing potential should agree to use adequate contraceptive measures from 2 weeks prior to the study and until 6 months after study treatment discontinuation.

12. Male patients who are willing to use barrier contraception (ie, condoms) for the duration of the study and for 3 months after study treatment discontinuation.

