4.5.1 Women of childbearing potential

Women of childbearing potential (WoCBP) may be included only if acceptable contraception is in place for 2 weeks before commencing study treatment, for the duration of the study, and for 6 months after the last dose of study drug.

WoCBP is defined as women between menarche and menopause who have not been permanently or surgically sterilized and are capable of procreation.

All WoCBP must have a negative pregnancy test during screening and within 3 days prior to starting each treatment cycle.

Male patients who are involved in the study must agree to avoid procreative and unprotected sex (ie, using acceptable forms of contraception as described in [Appendix G](#)) and must not donate sperm during the study and for 6 months after the last dose of study drug. Where the female partner is pregnant or not using effective birth control, men should be advised to abstain while in the study and for 6 months after the last dose of study drug.

Female partners, who are of childbearing potential, of men participating in the study will also be required to use effective contraceptive measures (detailed in [Appendix G](#)) while their partner is on study drug and for 6 months thereafter.

Because of the possibility of irreversible infertility due to therapy with carboplatin, male patients will be advised to arrange for the freezing of sperm samples prior to the start of the study should they wish to father children at a future date.

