13. Male patients must use a condom during treatment and for 6 months after the last dose of study drug(s) when having sexual intercourse with a pregnant woman or with a woman of childbearing potential. Female partners of male patients should also use a highly effective form of contraception (see Appendix G) for 6 months after the last dose of study drug(s) if they are of childbearing potential.

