2. ACCEPTABLE CONTRACEPTION METHODS

Highly effective method of birth control is defined in Note 3 in ICH Guidance M3 (Nonclinical Safety Studies for the Conduct of Human Clinical Trials for Pharmaceuticals) as one that results in a low failure rate (eg, <1% per year) when used consistently and correctly.

Note that women should have been stable on their chosen method of birth control for a minimum of 2 weeks before entering the trial. Generic names and examples of trade names are given. As trade names may vary, investigators should check the generic name of any contraception to ensure suitability.

Acceptable Non-hormonal birth control methods include:

- Vasectomised sexual partner PLUS male condom. With participant assurance that partner received post-vasectomy confirmation of azoospermia.
- Total sexual abstinence. Abstinence must continue for the total duration of study treatment and for at least 1 month after the last dose for female study subjects, and for 6 months after last dose for male study subjects. Periodic abstinence (eg, calendar ovulation, symptothermal post ovulation methods) and withdrawal are not acceptable methods of contraception.
- Tubal occlusion PLUS male condom
- Intra-uterine Device (IUD) - provided coils are copper-banded plus male condom

Acceptable hormonal methods:

- Normal and low dose combined oral pills PLUS male condom
- Cerazette (desogestrel) PLUS male condom. Cerazette is currently the only highly efficacious progesterone based pill.
- Hormonal shot or injection (eg., Depo-Provera) PLUS male condom
- Etonogestrel implants (e.g., Implanon, Norplant) PLUS male condom
- Norelgestromin / ethinylestradiol transdermal system PLUS male condom
- Intrauterine system [IUS] device (eg., levonorgestrel releasing IUS -Mirena®) PLUS male condom
- Intravaginal device (e.g., ethinylestradiol and etonogestrel) PLUS male condom
- Cerazette (desogestrel) plus male condom. Cerazette is currently the only highly efficacious progesterone based pill

The following methods are considered not to be highly effective and are therefore not acceptable contraceptive methods in AstraZeneca clinical trials:

- Triphasic combined oral contraceptives (COCs)
- All progesterone only pills except Cerazette
- All barrier methods, if intended to be used alone
- Non-copper containing Intra-Uterine Devices (IUDs)

- Fertility awareness methods
- Coitus interruptus

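### Arm B inclusion criterion 12 accepts men on 3 months of contraception after treatment, but the same arm's section 4.5.1 requires 6 months after the last dose.

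*Protocol*

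**What the plan says.** **Appendix B, section 4.1, criterion 12** admits men who are "willing to use barrier contraception (ie, condoms) for the duration of the study and for 3 months after study treatment discontinuation".

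**Appendix B, section 4.5.1** is headed for women of childbearing potential but also carries the rules for men. It says "Male patients who are involved in the study must agree to avoid procreative and unprotected sex", and the same sentence continues that they "must not donate sperm during the study and for 6 months after the last dose of study drug". For a man whose partner is already expecting or lacks reliable contraception, the section adds: "men should be advised to abstain while in the study and for 6 months after the last dose of study drug". A separate rule makes female partners who could conceive use contraception "while their partner is on study drug and for 6 months thereafter".

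**Appendix B, section 4** makes the inclusion list binding: "Under no circumstances can there be exceptions to this rule".

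**Appendix B, section 7.2.2 (paternal exposure)** gives no period. Section 7.7.2 of the master protocol sends the reader to the arm for the period.

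**Appendix G, section 2** sets the abstinence period at "for 6 months after last dose for male study subjects".

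**The concern.** Two current sections of one sub-protocol give different periods for the same protective measure, and the shorter one sits in the list that sites screen against. A man prepared to use condoms for 3 months after treatment, but not for 6, satisfies criterion 12 as written and would then breach section 4.5.1. A site that counsels from the eligibility list may also tell a man that he can stop at 3 months.

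The stake is fetal exposure in partners of men treated with AZD1775 and carboplatin. Nothing in the response or survival analyses depends on it.

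**Working it through.** There is no figure to reproduce. The check sets the stated periods side by side.

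| Source (Appendix B unless noted) | Who | Period after treatment | Counted from |
|---|---|---|---|
| 4.1, criterion 12 | Men, condoms | 3 months | Treatment discontinuation |
| 4.5.1 | Men, unprotected sex and sperm donation | 6 months | Last dose |
| 4.5.1 | Men, abstinence if partner pregnant or unprotected | 6 months | Last dose |
| 4.5.1 | Female partners of male patients | 6 months | Partner's time on study drug |
| 4.1, criterion 11 | Women in the trial | 6 months | Treatment discontinuation |
| 4.5.1 | Women in the trial | 6 months | Last dose |
| 7.2.2 | Partner pregnancies | none given | – |

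**Nominal gap.** 6 − 3 = 3 months, and 3 / 6 = 50% of the required period.

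**Do the different starting points explain it?** Treatment discontinuation can fall later than the last dose, which would narrow the gap. Under section 8.1.1 AZD1775 is taken on Days 1 to 3 of a 21-day cycle, so the next dose is due on Day 22. Section 7.3 requires discontinuation if a toxicity delay exceeds 28 days from the intended next dose, unless the Study Physician approves continuation. That puts the latest ordinary discontinuation at Day 22 + 28 = Day 50, which is 50 − 3 = 47 days after the last dose. Three months is at most 92 days, so criterion 12 then runs to 92 + 47 = 139 days after the last dose. Six months is at least 181 days. In this extreme case 181 − 139 = 42 days remain uncovered. The starting points can shrink the gap but cannot close it.

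**Does the 6 months attach only to sperm donation?** The first sentence on men in section 4.5.1 could be read that way, because the period stands at its end. The next two statements remove the ambiguity. Each sets 6 months for conduct that has nothing to do with donation: abstinence in one, partner contraception in the other. The partner rule also points to Appendix G for its methods. There every listed method other than total abstinence is paired with a male condom, and barrier methods used alone are rejected. Followed through its own cross-reference, section 4.5.1 asks for condom use for 6 months.

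**Which figure is the odd one out?** In the same inclusion list, women's eligibility wording says 6 months and agrees with section 4.5.1. Only the line for men disagrees.

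**The case against.** The strongest reply is that the 6-month protection is not missing. Section 4.5.1 binds every man in the study, and criterion 8 requires willingness to comply with study and follow-up procedures. Since all criteria must be met, a man who openly refuses 6 months could be turned away under criterion 8. This has some force: the defect is a contradictory criterion, not an absent safeguard. But criterion 8 is general, and section 4.5.1 speaks to men already in the study. A site should not have to use a general clause to override a specific one that says 3 months.

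Second, the supporting evidence outside Arm B is weak, and this is right. Appendix G's abstinence periods are generic: the same sentence gives women 1 month, which does not match Arm B's 6. Arm C asks men for 6 months in its own inclusion criteria, but for different drugs, and Arm A uses 180 or 90 days depending on regimen. None of this shows what is right for AZD1775 with carboplatin, and the protocol gives no rationale for either period. The case rests on criterion 12 against section 4.5.1.

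Third, criterion 12 also covers the duration of the study, and survival follow-up runs to its end. Read literally, that could cover much of the gap. It would also make the added 3 months redundant for most men, so it is unlikely to be the meaning.

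Finally, the numbers are small. Appendix B (section 2.6) plans up to 20 eligible patients and does not say how many would be men. Appendix A (section 2.7.3) puts median survival in this population below 6 months, so not every man would live into the uncovered interval.

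**Conclusion.** The inconsistency is real, and criterion 12 should be corrected. It asks for 3 months where the arm's own restrictions ask for 6, and no other Arm B section resolves the difference. The nominal shortfall is 3 months, half of the required period. In the extreme case worked above it is still about 6 weeks.

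Two assumptions matter. The first is that section 4.5.1, which states 6 months three times for men and their partners, gives the intended period; the alternative would be to shorten section 4.5.1, for which the protocol offers no support. The second is that sites screen men against the inclusion list as written. This is an internal inconsistency in a safety rule and leaves the response endpoint, the analysis sets and the interim decision unchanged. It merits correction, but it does not put the trial's conclusions in doubt.

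**What to change.** Reword Appendix B criterion 12 so that male patients must agree to contraception and to no sperm donation during the study and until 6 months after the last dose of study drug, using the methods in section 4.5.1 and Appendix G. Check that the Arm B consent form gives the same period. Optionally, add to Appendix G that the abstinence period is the one stated in the relevant arm appendix, since its generic periods do not match every arm.

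The cost is one line of protocol wording and a check of the consent form. Design, sample size and analysis do not change.
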